3.3 Subject Compensation

Subjects will accrue compensation for every visit according to the below table. They will be provided with a check based upon their compensation as of visits 7 and 14. If they were to attend every visit, their total amount would be \$300.

Visit	Amount
1	\$25
2	\$50
3-7 (each)	\$10
8	\$50
9-12 (each)	\$10
13	\$35
14	\$50

3.4 Randomization

We will use computer randomization to assign subjects to one of two possible treatment groups. The randomization procedure will be stratified by gender. A randomization procedure will be implemented using an Excel spreadsheet. As a participant is identified and enrolled on study, the study coordinator will ascertain gender, which will determine the next randomization.

A: subjects will consume 9g of EAA mixture supplement twice daily for 12 consecutive weeks.

B: subjects will consume 9g of placebo twice daily for 12 consecutive weeks.

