If not performed at visit 1, the physical exam will be performed at this visit. Randomization will be performed as mentioned below. The following assessments will be performed: functional (6-minute walk distance), SF-36 health questionnaire, a whole-body DEXA scan for lean mass measurement, strength (Cybex testing of maximal voluntary contraction of each leg; bilateral hand grip strength). Subjects will be provided with forms and training for recording their dietary intake over a 3-day period during the next week. Study staff will dispense approximately 10 days' worth of study product and a consumption diary for subjects to complete after ingesting each dose. Future visits will be scheduled.

Visits 3-7: Subjects will come to the IOA weekly to return their urine samples, empty supplement containers and consumption diary. They will be asked about any adverse events since last visit. Study staff will dispense more study product and a consumption diary.

Visit 8: Subjects will be asked about any adverse events since last visit. They will return their empty supplement containers and consumption diary. In no particular order, the following assessments will be performed: strength (Cybex testing of maximal voluntary contraction of

each leg; bilateral hand grip strength), functional (6-minute walk distance), SF-36 health questionnaire. Study staff will dispense more study product, a consumption diary, and another 3-day diet diary.

Visits 9-12: Subjects will come to the IOA weekly to return their empty supplement containers and consumption diary. They will be asked about any adverse events since last visit. Study staff will dispense more study product and a consumption diary.

Visit 13: Subjects will come to the IOA to return their empty supplement containers and consumption diary. They will be asked about any adverse events since last visit. Study staff will dispense more study product and a consumption diary. Subjects will be provided with a drink containing 30mg of a stable isotope of creatine (D-3, Cambridge Isotopes Laboratory, Tewksbury, MA). They will be asked to collect 3 separate urine samples over the next 48 hours at approximately 24-hour intervals and return them to UAMS at their next visit. Subjects will be issued a stool sample collection kit to use just prior to visit 14 and another 3-day diet diary.

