3.5 Blinding

This is a double-blinded study. EAA mixture will be provided by Prinova Inc. (Carol Stream, IL). Placebo will be purchased from online or local sources (Pure Protein website, Wal-Mart, etc.). Product containers will be coded so that only the unblinded study staff will know product

identity. After all study visits have been performed and all data entered into a database, the blind will be broken. Although the study products differ in taste, subjects will not be told which products are offered in which flavors.

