3.6 Study Products

The active study product is 9g twice a day of EAA mixture, a proprietary formula of Essential Blends, LLC (Fairbanks, AK). Product is a blend of amino acids, flavorings, caffeine and sweeteners (see Appendix) in powder form; packaged in 200g sealed containers. Subjects will dissolve 1 scoop of supplement into ~7 ounces of water and stir/shake until fully dissolved. They will be provided with shaker cups free of charge. Servings will be ingested between meals so that they ingest 2 servings per day. EAA mixture is currently available in only one flavor (lemon/lime).

The placebo product is 9g twice a day of Pure Protein 100% Whey protein (Worldwide Sport Nutritional Supplements, Inc., Bayport, NY). Unblinded study staff will repackage this product into 200g sealed containers which contain the appropriate scoops. See appendix for product information. Subjects will dissolve 1 scoop of supplement into ~7 ounces of water and stir/shake until fully dissolved. Servings will be ingested between meals so that they ingest 2 servings per day.

Subjects will be asked to save empty containers and return them to the study site for accountability purposes. Storage of both products is in a dry area at room temperature. Containers will be labelled identically, with the only difference being the study product code (A or B); the key to which is known only to the unblinded study staff until blinding has been broken at the end of data analysis.

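### Two shared container codes, an A/B key that section 3.4 appears to print, and an allocation list with no stated custodian leave blinding and allocation concealment unprotected

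*Combined protocol and SAP*

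**What the plan says.** The randomisation plan is section 3.4. It states "We will use computer randomization to assign subjects to one of two possible treatment groups", then "The randomization procedure will be stratified by gender" and "A randomization procedure will be implemented using an Excel spreadsheet". At enrolment, "the study coordinator will ascertain gender, which will determine the next randomization". It does not state who generates, holds or opens the spreadsheet, whether later rows are hidden, or whether blocks are used.

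The same section then defines the arms by letter: "A: subjects will consume 9g of EAA mixture supplement twice daily for 12 consecutive weeks", with B as the placebo arm.

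Section 3.6 says the containers look alike, "with the only difference being the study product code (A or B", and that only unblinded staff know the key until the blind is broken. Section 3.5 opens its last sentence with "Although the study products differ in taste" and says that subjects will not be told which product comes in which flavour. Section 3.6 gives the EAA mixture a single flavour, lemon/lime. Appendix 11.1 gives the placebo as Vanilla Creme.

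For Visit 2, section 3.1 reads "Randomization will be performed as mentioned below. The following assessments will be performed", and the list that follows contains the 6-minute walk, the leg and grip strength tests and the SF-36. Section 7.1 uses the baseline measures as a covariate.

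**The concern.** With two codes and two products, the blind depends on one piece of information. Once anyone learns what A is, B follows, and the product of every subject whose code is visible is known. The opportunities recur. Subjects return containers at weekly visits, where section 3.2 has staff weigh them, and a remark about lemon or vanilla is enough for anyone who has read the protocol.

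Two things are at stake. The first is blinded assessment: walk distance and strength depend on effort, and an assessor who knows the product may encourage subjects differently. The second is concealment: if enrolling staff can see the list and the codes have been decoded, the next assignment is known when a subject is being enrolled or tested at baseline. That could influence who enters and how hard a subject is pushed on the measure later used as covariate. Adjustment for baseline, gender and lean mass does not repair either problem.

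A smaller matter is that section 7.3 needs 30 completers per group, and no mechanism for holding the arms near 1:1 is described.

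**Working it through.** **1. The codes, section against section.**

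| Source | What it establishes |
|---|---|
| 3.6 | Containers differ only by A or B; key confined to unblinded staff |
| 3.4 | Arm A is the EAA mixture, arm B the placebo |
| 3.5, 3.6, Appendix 11.1 | Products differ in taste: lemon/lime against Vanilla Creme |

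Either the arm letters in 3.4 are the container codes, and the protocol discloses the key that 3.6 restricts, or they are unrelated, and the text does not say so. In both cases one decoded container decodes all subjects, up to 80. With subject-specific numbers it would decode one.

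**2. The plan's own power figure.** Inputs from Table 4 and section 7.4: 30 per group, α = 0.025 (two-sided reproduces the table), d = mean change / SD. Noncentral t with n₁+n₂−2 = 58 df and noncentrality d·√(n₁n₂/(n₁+n₂)) = d·√15.

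| Endpoint | d | Recomputed | Stated |
|---|---|---|---|
| 6-minute walk | 105.1/89.3 = 1.177 | 98.67% | 98.67% |
| Leg strength | 11.0/13.3 = 0.827 | 81.38% | 81.31% |
| Grip strength | 4.1/4.6 = 0.891 | 87.19% | 87.19% |
| Gait speed | 0.23/0.28 = 0.821 | 80.80% | 80.80% |

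At d = 0.82 exactly, power is 80.7%. The plan's figures are reproduced.

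**3. Chance imbalance, assuming unrestricted allocation.** The text is silent on blocks, so this is an assumption. With X ~ Binomial(60, 0.5):
- P(X = 30) = C(60,30)/2⁶⁰ = 10.3%
- P(26:34 or worse) = 2·P(X ≤ 26) = 36.6%
- P(25:35 or worse) = 2·P(X ≤ 25) = 24.5%

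**4. What imbalance costs in power at d = 0.82.**

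| Split | Noncentrality | Power |
|---|---|---|
| 30:30 | 0.82·√(900/60) = 3.176 | 80.7% |
| 26:34 | 0.82·√(884/60) = 3.147 | 79.9% |
| 25:35 | 0.82·√(875/60) = 3.131 | 79.4% |
| 22:38 | 0.82·√(836/60) = 3.061 | 77.4% |

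Averaged over all binomial splits, power is 79.9%. The loss is 80.7 − 79.4 = 1.3 points at 25:35.

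**5. What blocking can and cannot do.** The 30 per group are completers, 60 out of up to 80 enrolled (section 3.0), which implies attrition of up to 1 − 60/80 = 25%. From an exact 40:40 split with 60 random completers (hypergeometric), 26:34 or worse falls from 36.6% to 6.9%, but exactly 30:30 still occurs only 20.3% of the time. By simulation with 80 enrolled and 25% random attrition, both arms reach 30 completers in about 34% of trials from 40:40, against about 19% with unrestricted allocation.

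**6. Blocking and predictability.** For someone who sees past codes and guesses the arm that is behind, simulated success is 50% with no blocks, about 68% with fixed blocks of 6 and about 71% with fixed blocks of 4. Blocking therefore makes concealment more important.

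**The case against.** The strongest reply is that much of this is silence. A reader might infer that the coordinator runs the spreadsheet. Section 3.4 says only that the coordinator ascertains gender, and sections 3.5 and 3.6 establish unblinded staff who could be the ones reading the list. That stands: the documents neither give the coordinator the list nor keep it from the coordinator.

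A reader might also infer that assignments are predictable because no blocks are mentioned. This is wrong on two counts: silence is not a statement that blocks are absent, and unrestricted allocation is the hardest to guess. Any prediction risk comes from a visible list and decodable codes.

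Nor does section 3.1 state that randomisation precedes the baseline tests. It is a narrative list, and the Table of Events has no randomisation row. What stands is that the order is unprotected.

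On balance, it is fair to say that a t-test does not need equal arms, that the power loss is small, and that section 7.1 already has gender in the model. Blocking would not deliver 30 completers per group either.

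Finally, the A and B in section 3.4 may be arm labels only. Even so, the two shared codes and the distinguishable flavours remain. Withholding flavour information from subjects does not help when staff can read both flavours in the protocol.

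**Conclusion.** The concern holds as a weakness of blinding and concealment. On the documents' own text there are two shared codes, two distinguishable flavours, and a section that pairs A and B with products although another restricts that pairing to unblinded staff. That the protocol discloses the key is conditional on the arm letters being the container codes. That one unmasking reaches every subject is not conditional on this.

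Selection bias would further require a visible list and someone acting on it. The documents establish neither, and its size cannot be computed from them. The separation of enrolment from the list, and of randomisation from the baseline tests, is undescribed; no breach is shown.

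The imbalance part is minor. The 10.3%, 36.6% and 24.5% figures assume unrestricted allocation, and the power cost is about 1 point at 25:35. This is a recommended, inexpensive improvement and does not invalidate the design.

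**What to change.** 1. Replace the A/B container labels with subject-specific container numbers. Remove the product assignment of A and B from section 3.4, or state that those letters are unrelated to the container codes, so that 3.4 and 3.6 agree.
2. State in section 3.4 that the existing unblinded staff generate and hold the list, and that enrolling staff and assessors have no access to it. The coordinator sends subject number and gender and receives a container number.
3. State in section 3.1 that a number is released only after eligibility is confirmed and all Visit 2 baseline tests are complete, and add a randomisation row to the Table of Events.
4. If the list is not already blocked, use permuted blocks of varying size within gender, with sizes undisclosed to enrolling staff. As an illustration, blocks of 4 limit imbalance to 2 per gender and 4 overall. At 60 randomised the worst split is then 28:32, with power 80.5% if all complete. Do this only with the list concealed.

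The cost is individual labelling and some extra coordination at Visit 2. It uses staff the trial already has and needs no added subjects. It should be in place before subjects are randomised, because analysis cannot restore concealment afterwards.

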3.5 Blinding

This is a double-blinded study. EAA mixture will be provided by Prinova Inc. (Carol Stream, IL). Placebo will be purchased from online or local sources (Pure Protein website, Wal-Mart, etc.). Product containers will be coded so that only the unblinded study staff will know product

identity. After all study visits have been performed and all data entered into a database, the blind will be broken. Although the study products differ in taste, subjects will not be told which products are offered in which flavors.

3.6 Study Products

The active study product is 9g twice a day of EAA mixture, a proprietary formula of Essential Blends, LLC (Fairbanks, AK). Product is a blend of amino acids, flavorings, caffeine and sweeteners (see Appendix) in powder form; packaged in 200g sealed containers. Subjects will dissolve 1 scoop of supplement into ~7 ounces of water and stir/shake until fully dissolved. They will be provided with shaker cups free of charge. Servings will be ingested between meals so that they ingest 2 servings per day. EAA mixture is currently available in only one flavor (lemon/lime).

The placebo product is 9g twice a day of Pure Protein 100% Whey protein (Worldwide Sport Nutritional Supplements, Inc., Bayport, NY). Unblinded study staff will repackage this product into 200g sealed containers which contain the appropriate scoops. See appendix for product information. Subjects will dissolve 1 scoop of supplement into ~7 ounces of water and stir/shake until fully dissolved. Servings will be ingested between meals so that they ingest 2 servings per day.

Subjects will be asked to save empty containers and return them to the study site for accountability purposes. Storage of both products is in a dry area at room temperature. Containers will be labelled identically, with the only difference being the study product code (A or B); the key to which is known only to the unblinded study staff until blinding has been broken at the end of data analysis.

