3.1 Study Visits

Visit 1: subjects will come to the UAMS IOA 3rd floor for informed consent discussion. Once consent is obtained, study staff will administer and score the SLUMS test for dementia. If subjects score >20 , subsequent study procedures will be performed. A medical history and list of current medications will be obtained (printed from Epic if they are a UAMS patient). Subject height, weight, body temperature and blood pressure will be measured. A blood sample will be drawn (approx. 15 mL) for criteria-related tests if recent results are not available from their medical record. A brief training session will take place where subjects will be introduced to the

isokinetic dynamometer (Cybex) machine and how it is used at the testing visits. They will undergo a practice test on one leg.

A physical exam will be performed at this visit or at visit 2. Based upon the results of the screening blood sample, visit 2 will be scheduled.

Visit 2: Subjects must come to this visit having fasted overnight. They will be asked about any adverse events since last visit. A fasting blood sample (~30 mL) will be drawn to determine baseline values (tests listed below), and a snack will be provided and coffee offered. A urine sample will be collected for dipstick proteinuria. Subjects will be asked to provide a stool sample, but if unable at this visit, they can take home a sample collection kit to use. They will be instructed to collect the stool sample at home on the day of Visit 2 or at UAMS. Subjects will be provided with a drink containing 30mg of a stable isotope of creatine (D-3, Cambridge Isotopes Laboratory, Tewksbury, MA) dissolved in water. They will be asked to collect 3 separate urine samples over the next 72 hours at approximately 24-hour intervals, place them into their freezer, and return them to UAMS at their next visit.

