Visit 14: Subjects must come to this visit having fasted overnight. They will be asked about any adverse events since last visit. They will return their diet records, empty supplement containers, any full supplement containers, their stool sample, and their consumption diary. Study staff will administer and score the SLUMS test for dementia. A fasting blood sample (~30 mL) will be drawn. After the blood sample is drawn, subjects will be offered a meal and beverages. A urine sample will be collected for dipstick proteinuria.

The following assessments will be performed: functional (6-minute walk distance), SF-36 health questionnaire, a whole-body DEXA scan for lean mass measurement, strength (Cybex testing of maximal voluntary contraction of each leg; bilateral hand grip strength). At the end of this visit, subject will have no further study visits.

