11.0 Appendices

11.1 Study Product Information

EAA mixture

His	3.5%
Ile	7.1%
Leu	14.3%
Lys	6.0%
Met	3.3%
Phe	8.8%
Thr	5.3%
Trp	1.4%
Val	9.25%
Glutamine	1.2%
Carnitine	2.9%
Nicotinamide	1.5%
Vitamin C	1.5%
Caffeine	0.6%
Sucralose and other flavorings and preservatives	28.3%

Placebo: Pure Protein – Vanilla Creme flavor

Directions: For adults, take one (1) scoop (39 g), one to two times daily. For maximum muscle support consume 1-2 scoops twice per day, with at least 1-2 scoops taken immediately after exercise.

Nutrition Facts

Serving Size 1 Scoop (39g)
Servings Per Container about 23

Amount Per Serving		
Calories 150		Calories from Fat 25
		%Daily Value*
Total Fat 2.5g		4%
Saturated Fat 1g		5%
Trans Fat 0g		
Cholesterol 80mg		27%
Sodium 100mg		4%
Potassium 160mg		5%
Total Carbohydrate 8g		3%
Dietary Fiber 0g		0%
Sugars 2g		
Protein 25g		50%
Vitamin A 0%		Vitamin C 0%
Calcium 20%		Iron 0%
Phosphorus 10%		Magnesium 4%

*Percent Daily Values are based on a 2,000 calorie diet. Your daily values may be higher or lower depending on your calorie needs:

	Calories:	2,000	2,500
Total Fat	Less than	65g	80g
Sat Fat	Less than	20g	25g
Cholesterol	Less than	300mg	300mg
Sodium	Less than	2,400mg	2,400mg
Potassium		3,500mg	3,500mg
Total Carbohydrate		300g	375g
Dietary Fiber		25g	30g
Protein		50g	65g

Calories per gram:
Fat 9 • Carbohydrate 4 • Protein 4

INGREDIENTS: Protein Blend (Ultrafiltered Whey Protein Concentrate [which contains Beta-lactoglobulin, Alpha-lactalbumin and Glycomacropeptides], Microfiltered Whey Protein Isolate), Maltodextrin, Natural and Artificial Flavors, Cellulose Gum, Soy Lecithin, Xanthan Gum, Dicalcium Phosphate, Calcium Carbonate, Acesulfame Potassium, Sucralose.

Contains milk and soy ingredients.

Typical Amino Acid Profile (milligrams per 39 g scoop**)			
Essential Amino Acids		Nonessential Amino Acids	
Histidine	490 mg	Alanine	1,139 mg
Isoleucine	1,460 mg	Arginine	640 mg
Leucine	2,531 mg	Aspartic Acid	2,980 mg
Lysine	2,127 mg	Cysteine	601 mg
Methionine	562 mg	Glutamic Acid	3,919 mg
Phenylalanine	808 mg	Glycine	444 mg
Threonine	1,783 mg	Proline	1,415 mg
Tryptophan***	485 mg	Serine	1,299 mg
Valine	1,376 mg	Tyrosine	728 mg

***L-tryptophan is naturally occurring, not added.
**approximate values

©2014 Carefully Manufactured by
Worldwide Sport Nutritional Supplements, Inc.
Bayport, NY 11705

For questions or reorders call:
[name]
or visit our website at
www.pureprotein.com

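### Only the EAA product lists caffeine, and Visit 8 sets no food, coffee or time-since-serving condition before the walk and strength tests, so a same-day stimulant effect could enter the midpoint comparison between arms

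*Combined protocol and SAP*

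**What the plan says.** **Products.** Section 3.6 describes the active product: "Product is a blend of amino acids, flavorings, caffeine and sweeteners". The amount is given as: "The active study product is 9g twice a day of EAA mixture". Section 11.1 lists caffeine at 0.6% of the mixture and does not say whether that is by weight. The comparator label in the same section lists whey proteins and maltodextrin, then "Natural and Artificial Flavors, Cellulose Gum, Soy Lecithin, Xanthan Gum, Dicalcium Phosphate, Calcium Carbonate, Acesulfame Potassium, Sucralose"; caffeine does not appear. On timing, Section 3.6 says only this, for both products: "Servings will be ingested between meals so that they ingest 2 servings per day".

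**Test visits (Section 3.1 and the Table of Events).**
- Visit 2: overnight fast and blood draw, then "a snack will be provided and coffee offered". The walk and strength tests are done at this visit. Product is first dispensed here, so baseline carries no product caffeine.
- Visit 8: "In no particular order, the following assessments will be performed", covering strength, walk and SF-36. No fasting, food, coffee or serving-time instruction is given, and the Table of Events marks fasting at Visits 2 and 14 only.
- Visit 14: overnight fast and blood draw, after which "subjects will be offered a meal and beverages". The walk and strength tests are done at this visit.

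**Control and analysis.** The consumption diary is completed after each dose, but nothing links its entries to test times. Section 4.2 restricts outside protein and amino acid supplements and does not mention caffeine. The Section 7.1 model has treatment, time, their interaction, baseline, lean body mass and gender. Section 7.2 tests the arms separately at midpoint and final, at 2.5%, if the interaction is significant.

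**The concern.** The walk and strength endpoints depend on effort, and Hypothesis 1 concerns the effect of 12 weeks of regular consumption. At Visit 8 a subject in the EAA arm may be tested shortly after a caffeinated serving, and a control subject after one with no listed caffeine. Randomisation does not balance this, because the difference lies in the product itself. Any acute effect would add to the Visit 8 difference between arms and could be read as an early gain in function. If it is present at Visit 8 and absent at the fasted Visit 14, it also has the shape of a treatment-by-time interaction, which decides which tests are run. With timing unrecorded, the question could not be settled after the visits.

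**Working it through.** **1. The plan's own figures.** Table 4 (Section 7.4): 30 per group, alpha 2.5%, effect size = mean change / SD of change, two-sample t-test. Computed two-sided from the noncentral t distribution:
- 6-minute walk: 105.1 / 89.3 = 1.18, power 98.67% (stated 98.67%)
- leg strength: 11.0 / 13.3 = 0.83, power 81.38% (stated 81.31%)
- grip strength: 4.1 / 4.6 = 0.89, power 87.19% (stated 87.19%)
- gait speed: 0.23 / 0.28 = 0.82, power 80.80% (stated 80.80%)

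The table reproduces and is not in dispute. The same test is used below.

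**2. Caffeine by arm.** 9 g × 0.6% = 54 mg per serving; × 2 = 108 mg/day. The listed EAA components sum to 94.95%; rescaled to 100%, 9,000 mg × 0.6 / 94.95 is about 57 mg per serving. Comparator: none listed.

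**3. Assumed shift at Visit 8.** No acute effect size is given, so a range is assumed, in SDs of change. With the Table 4 walk SD of 89.3:
- 0.1 × 89.3 = 8.9
- 0.2 × 89.3 = 17.9
- 0.3 × 89.3 = 26.8

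Against the hypothesised 105.1 these are about 8%, 17% and 25%. They are shifts in the arm mean: 0.2 SD would need, for example, half the EAA arm tested soon after a serving with an individual effect of 0.4 SD (0.5 × 0.4 = 0.2).

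**4. Visit 8 test alone.** With no true treatment effect, 30 per arm and two-sided 2.5%, the rejection rate is 3.6%, 7.0% and 13.5%. Rejections in favour of EAA are 3.1%, 6.9% and 13.5%, against a nominal 1.25%. The plan does not run this test unconditionally, so these are not its error rates.

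**5. Interaction test.** Take the SD as 1 at midpoint and final, with an assumed correlation of 0.5. The midpoint-minus-final difference then has SD √(2 × (1 − 0.5)) = 1, so a shift at Visit 8 only keeps its size. At 5% the interaction is significant in 6.7%, 11.9% and 20.8% of trials.

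**6. The gated plan, by simulation.** t-test approximations, shift at Visit 8 only, correlation 0.5. If the interaction is significant at 5%, the Visit 8 test is run at 2.5%; otherwise the pooled main effect is tested at 5%.

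| Shift at Visit 8 (SD) | Significant interaction and significant Visit 8 test | False claim by the pooled or Visit 8 test |
|---|---|---|
| 0 | – | about 5.4% |
| 0.1 | about 1.1% | about 6.2% |
| 0.2 | about 2.8% | about 9.2% |
| 0.3 | about 6.6% | about 14.5% |

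A rerun of 400,000 trials per case agreed. Counting false Visit 14 claims after a significant interaction as well gave about 5.9%, 6.9%, 9.8% and 15.5%. For correlations from 0.25 to 0.75, the middle column at 0.3 SD stays between about 6% and 8%.

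**The case against.** - **The visit differences apply to both arms.** This stands. Food, coffee and fasting conditions are the same for EAA and control at each visit. Alone they add noise and affect within-group change. A reader might infer that they bias the randomised comparison; they do not. Coffee open to both arms could even dilute a caffeine contrast, so the net effect is uncertain.
- **The 12-week result is protected.** This largely stands. A reader might infer that the final comparison is equally exposed, but the Visit 14 overnight fast makes a same-morning serving unlikely, although it is not expressly excluded.
- **Caffeine is part of the product under test.** This stands for attribution: the trial compares whole products, so a caffeine contribution is not in itself an error. It does not answer whether a Visit 8 gain is sustained or lasts only hours after a serving.
- **The effect is assumed.** This stands. Nothing in the documents says that 54 mg changes walking or strength, or how many subjects take a serving before testing. This is a possible confounder, not a demonstrated one.
- **Test order is not stated.** This stands. That testing follows the snack at Visit 2 or the meal at Visit 14 is inferred from the order of the text.

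**Conclusion.** The point holds for Visit 8. Caffeine is listed in one arm only, and nothing in the plan controls, records or adjusts for the interval between a serving and the effort tests. A same-day effect could enter the midpoint comparison and contribute to a spurious interaction.

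The size is conditional. Visit 8 shifts of 0.1 to 0.3 SD raise the chance of a false claim from about 5.4% to about 6% to 15%. This rests on an assumed effect size, no true treatment effect, no shift at Visit 14, a mid-to-final correlation of 0.5, and t-tests standing in for the ANCOVA. The documents do not support a claim that the 12-week comparison is materially biased, or that a caffeine effect of any given size will occur. The case for acting is that the remedy is cheap and missing times cannot be recovered later.

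**What to change.** 1. Reconcile the Visit 2, 8 and 14 procedures in Section 3.1 into one set of test-day conditions: the same food state at each visit, and the walk and strength tests completed before the site offers coffee or any other caffeinated drink.
2. Record the time of the last study serving and of the last caffeine intake at Visits 8 and 14, and of the last caffeine intake at Visit 2.
3. Add to Section 7 a sensitivity analysis of the Visit 8 comparison using these times. Both arms take servings, so the arms can be compared at similar times since the last serving.
4. Have the sponsor state how servings on test days relate to testing, in the same words for both arms. This review does not propose that rule.

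Cost: visit wording, two CRF fields, one sensitivity analysis and slight inconvenience to subjects, mainly at Visit 8. Product amount, number of servings, sample size and the main model do not change.
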